## 4.2 Derived Endpoints: Calculation Methods

#### 4.2.1 Immunogenicity

#### 4.2.1.1 Computed Values for Analysis

In order to appropriately manage extreme values (< lower limit of quantification [LLOQ] and  $\geq$  upper limit of quantification [ULOQ]) for analysis purposes, the following computational rule is applied to the values provided in the clinical database for each blood sample drawn: For the computation of GMTs, any titer reported as < LLOQ will be converted to a value of LLOQ/2.

- For calculation of proportion of participants with NAb titers ≥ threshold of 10 (1/dil), a titer reported as < LLOQ will be converted to a value of LLOQ/2.
- For calculating geometric mean of titer ratio (GMTR), < LLOQ will be converted to LLOQ/2 for a numerator and < LLOQ will be converted to LLOQ for a denominator. If both numerator and denominator are < LLOQ, then both will be converted in the same way so that titer ratio=1.
- Any titer reported as > ULOQ will be converted to ULOQ.

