# 8.1.2.2 Immunogenicity Assessment Methods

# YF MN Method Description (all participants, visits V1 and V4 to V10 for the main cohort, and visits V1, V2, and V4 to V10 for the subset of participants)

YF NAb titers will be measured using a MN assay. Serial, 2-fold dilutions of serum to be tested (previously heat-inactivated) are mixed with a constant concentration of the YF vaccinal strain 17D. The mixtures are inoculated into wells of a 96-well microplate with permissive Vero cells and incubated for 2 days. A reduction in virus infectivity (viral antigen production) due to neutralization by antibody present in serum samples is detected by enzyme linked immunosorbent assay (ELISA). After washing and fixation, YF viral antigen production in cells is detected by successive incubations with a flavivirus-specific mAb, horse radish peroxidase anti-mouse immunoglobulin G (IgG) conjugate, and a chromogenic substrate. The resulting optical density is measured using a microplate reader. The reduction in YF virus infectivity as compared to that in the virus control wells constitutes a positive neutralization reaction indicating the presence of NAbs in the serum sample. The method was qualified by assessing precision, specificity, LLOQ, and dilutability. To verify the LLOQ of 10, a panel of 17 additional human serum samples diluted in a negative serum targeting a titer of ½ of the LLOQ to exactly the LLOQ was tested 11 times by 2 qualified analysts in 2 independent assay runs. This data supports that the LLOQ of 10 was verified for the YFV MN assay and LOD can be considered as equivalent to LLOQ (LOD = LLOQ):

- LLOQ determined as 10 (1/dil) with the MN assay defines the threshold of protection; a participant presenting with detectable Ab (≥ LLOQ) is considered as protected against YF virus
- As LOD = LLOQ, YF-naïve population, or YF negative population, corresponds to participants with no pre-existing Ab titers ie, no detectable as below LLOQ equal to 1:10. Those subjects are given a value equal to half LLOQ, ie, 5 (1/dil)
- Seroconversion is defined as having at least a 4-fold increase of Ab titers as compared to baseline (pre-vaccination value); Sanofi Pasteur would like to consider this 4-fold increase in Ab titers for both participants with or without pre-existing Ab titers.

o For participants assigned with a value at baseline of 10 (LLOQ) or more, 1/dil, seroconversion means values of 40, 1/dil, or more post-vaccination.

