# 4 Endpoints and Assessment Methods

## 4.1 Objectives, Endpoints and Assessment Methods

Objectives	Objectives Endpoints	
Primary		

 
Immunogenicity
 
To demonstrate the non- inferiority of the antibody response in terms of seroconversion rate 28 days after vaccine administration of one dose of vYF (administered on D01) compared to the antibody response after one dose of the Stamaril control vaccine (administered on D01) in YF-naïve participants enrolled in EU*
 
	Seroconversion rates will be assessed 28 days post-vYF (administered on D01) and post-Stamaril (administered on D01) using a YF microneutralization (MN) assay in participants enrolled in EU Seroconversion is defined as a 4-fold increase in NAb titers as compared to the pre-vaccination value. With a nominal value of half LLOQ, ie, 5 (1/dil), assigned to baseline YF seronegative participants, the seroconversion requires an increase to at least a titer of 20 (1/dil) on 28 day post-vaccination.	See Section 8.1.2 of the protocol.
Secondary		

 
Immunogenicity
 
To demonstrate the non- inferiority of the antibody response in terms of seroconversion rate 28 days after vaccine administration of one dose of vYF (administered on D01) compared to the antibody response after one dose of the Stamaril control vaccine (administered on D01) in EU YF-naïve participants with a time window of +3 days.
 
	• Seroconversion rates will be assessed 28 days (time window of +3 days) post-vYF (administered on D01) and post-Stamaril (administered on D01) in a YF MN assay in EU YF-naïve participants	See Section 8.1.2 of the protocol.
• To describe the antibody immune responses to YF in	YF antibody assessments will be performed using YF MN assay as	

Objectives	Endpoints	Assessment

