LLOQ determined as 10 (1/dil), also defined the threshold of protection.

‡ The following AESIs have been defined for this clinical development program based upon the prior experience with YF vaccines:

Serious hypersensitivity/allergic reactions

Organ failure/serious viscerotropic events

• Serious neurologic events

†A subset of the first 90 participants (60 participants in Group 1 and 30 participants in Group 2) enrolled in EU at some sites will provide an additional post-vaccination blood sample on D11 to assess the immune response elicited by both vaccines in terms of NAb titers.

A subset of the first 60 participants enrolled at some sites in Asia (40 participants in Group 1 and 20 participants in Group 2) will provide an additional post-vaccination blood sample on D11 to assess the immune response elicited by both vaccines in terms of NAb titers

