## 4.2.1.3 Seroconversion

See Section 4.1 (or Section 8.1.2 of the protocol).

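### The GMTR rule counts a below-LLOQ denominator as 10 where GMT and seroconversion count it as 5, and one protocol sentence breaks the 4-fold definition for baselines above 10

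*SAP*

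**What the plan says.** - **Assay limit.** SAP 4.1: "LLOQ determined as 10 (1/dil), also defined the threshold of protection".
- **GMT.** SAP 4.2.1.1: "For the computation of GMTs, any titer reported as < LLOQ will be converted to a value of LLOQ/2", that is, 5.
- **GMTR.** The same section: "< LLOQ will be converted to LLOQ/2 for a numerator and < LLOQ will be converted to LLOQ for a denominator", with one exception: "If both numerator and denominator are < LLOQ, then both will be converted in the same way so that titer ratio=1".
- **Seroconversion from a seronegative baseline.** SAP 4.1: "With a nominal value of half LLOQ, ie, 5 (1/dil), assigned to baseline YF seronegative participants", which it turns into a D29 threshold of 20. Protocol 8.1.2.2 agrees: "Those subjects are given a value equal to half LLOQ, ie, 5 (1/dil").
- **Seroconversion from a baseline at or above LLOQ.** Protocol 8.1.2.2 asks for at least a 4-fold rise, then adds: "For participants assigned with a value at baseline of 10 (LLOQ) or more, 1/dil, seroconversion means values of 40, 1/dil, or more post-vaccination".
- **SAP derivation of seroconversion.** SAP 4.2.1.3 is only a cross-reference: "See Section 4.1 (or Section 8.1.2 of the protocol").
- **Reference visits.** Under SAP 5.1.2.2, D11, D29 and M6 are compared with D01, and Y1 to Y5 each with the planned visit before. The conversions in SAP 4.2.1.1 cover GMT, the proportion at or above 10, and GMTR. No text says what a previous-visit titre below LLOQ counts as when seroconversion is derived from Y1 onwards.

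**The concern.** The same D01 sample takes two values in one set of outputs. All YF-naive participants have D01 below LLOQ by definition, so the denominator exception governs the D01-based ratio of every naive responder. SAP Tables 7.2 and 7.3 print GMTs and GMTRs in one block, and a reader who divides one GMT by another will not recover the GMTR. The seroconversion tables will also count as 4-fold responders some participants whose recorded titre ratio is between 2 and 4. The rule treats rises and falls across the LLOQ differently, which matters for the yearly persistence ratios.

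The 40-or-more sentence is a second, independent problem. Read literally, it credits seroconversion to participants whose titre has not risen 4-fold or has not risen at all. Seroconversion by YF-immune status is a planned output (SAP Table 7.4).

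**Working it through.** **1. Reproduce the stated threshold.** LLOQ = 10, and a seronegative baseline counts as LLOQ/2 = 5. Then 4 × 5 = 20, the threshold in SAP 4.1 and Protocol 8.1.2.2. By contrast, 4 × LLOQ = 4 × 10 = 40, the threshold that a baseline value of 10 would give.

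**2. Individual D01-based ratios for a naive participant.**

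| Later titre | SAP GMTR rule | LLOQ/2 in both positions | Seroconverted (≥ 20)? |
|---|---|---|---|
| < 10 | 1 | 5/5 = 1 | no |
| 10 | 10/10 = 1 | 10/5 = 2 | no |
| 20 | 20/10 = 2 | 20/5 = 4 | yes |
| 40 | 40/10 = 4 | 40/5 = 8 | yes |
| 320 | 320/10 = 32 | 320/5 = 64 | yes |

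The ratio is halved whenever the later titre is at or above LLOQ and unchanged when both titres are below it. A rise from below 10 to 10 scores the same as no change.

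**3. Group GMTR.** Let f be the share of naive participants with a post-vaccination titre at or above LLOQ. On the log2 scale the SAP ratio is lower by 1 for that share and by 0 for the rest. The mean log ratio therefore falls by f, and the GMTR is multiplied by 2^(−f). Every naive D01 value is 5 in the GMT, so GMT(D01) = 5. With LLOQ/2 in both positions the GMTR equals GMT(later)/GMT(D01); under the SAP rule it is that ratio times 2^(−f). The documents do not give f, so the values below are assumptions:

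| f | 100% | 99% | 95% | 90% | 75% | 50% | 25% |
|---|---|---|---|---|---|---|---|
| Factor | 0.500 | 0.503 | 0.518 | 0.536 | 0.595 | 0.707 | 0.841 |

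At D29 and M6 the factor is near 0.5 if nearly all respond. At D11 it could be closer to 1. If the arms differ in f, the factor differs too: 75% against 50% gives 2^(−0.75)/2^(−0.50) = 2^(−0.25) = 0.841, to the disadvantage of the arm with more responders.

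**4. Yearly ratios (Y1/M6 to Y5/Y4).** None uses D01. They change only when the earlier titre is below LLOQ and the later one is at or above it, and then always downward. Path 10, < 10, 10: the SAP gives 5/10 = 0.5, then 10/10 = 1.0, a product of 0.5. LLOQ/2 in both positions gives 0.5, then 10/5 = 2, a product of 1, which matches the unchanged titre.

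**5. The 40-or-more sentence.**

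| Baseline | 4-fold requires | Ratio at a titre of 40 | Passes the literal sentence? |
|---|---|---|---|
| 10 | 40 | 4 | yes, correctly |
| 20 | 80 | 2 | yes |
| 40 | 160 | 1 | yes |
| 80 | 320 | 0.5 | yes |

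It agrees with the 4-fold definition only at a baseline of exactly 10.

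**6. Primary test.** The objective is limited to YF-naive participants in EU, the threshold of 20 is written out, and the PPAS excludes anyone who is not YF-naive. Neither rule enters the primary comparison.

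**The case against.** A titre below 10 is censored, and 5 is no more its true value than 10 is. Using LLOQ as the denominator gives the smallest fold-rise consistent with a quantifiable later titre. That is a recognisable conservative convention, prespecified and the same in both arms. GMTR is secondary and descriptive with no hypothesis attached. This stands: the choice can be defended, but neither document states or defends it, and the mismatch with the GMTs remains without a footnote.

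On the 40-or-more sentence, its parent bullet requires a 4-fold rise with or without pre-existing antibody. The sentence can be read as an illustration at the LLOQ. SAP 4.2.1.3 names SAP 4.1 first, and 4.1 contains no such rule. Few flavivirus-experienced participants are expected in EU (Protocol 4.2). This also stands in part: inflated YF-immune seroconversion is a risk under the literal reading, not a certain result.

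A reader might go further and infer that seroconversion will be derived from the GMTR ratio, so that the primary threshold moves from 20 to 40, the value Protocol 2.1 footnotes for VYF01. The documents do not support that. SAP 4.2.1.1 confines the LLOQ denominator to the GMTR, and the threshold of 20 is explicit. Even under such miscoding the rule would apply to both arms. The primary difference would move by the between-arm difference in the share with titres from 20 to below 40, not by the vYF share alone.

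**Conclusion.** The inconsistency is real and confined to descriptive secondary endpoints. The D01-based ratio is halved for each YF-naive participant with a quantifiable later titre, and the group GMTR is multiplied by 2^(−f), at most a 2-fold shortfall against the GMTs beside it. The factor rests on the rule being programmed as written; the value of f is assumed.

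Two broader readings do not hold. Not every YF-naive GMTR is halved: the ratio is 1 when both titres are below LLOQ, and the yearly ratios do not use D01. Nor does a 2-fold rise count as seroconversion: under the seroconversion rule, 20 against 5 is 4-fold, and no naive participant is misclassified.

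The 40-or-more sentence contradicts its own 4-fold definition for every baseline above 10 and can reach the YF-immune seroconversion results through the cross-reference.

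The non-inferiority conclusion is unaffected as written. SAP 5.1.1.1 also runs the primary analysis on the FAS; the same holds there provided that it is kept to the YF-naive participants named in the objective. Severity: minor to moderate.

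**What to change.** 1. **SAP 4.2.1.1.** Use LLOQ/2 for a below-LLOQ titre in both numerator and denominator of the GMTR. If the LLOQ denominator is kept as a conservative convention, say so, and footnote Tables 7.2 and 7.3: the naive GMTR is a minimum fold-rise where the later titre is quantifiable, and it does not equal the ratio of the GMTs shown.
2. **SAP 4.2.1.3.** Replace the bare cross-reference with a rule: post-vaccination titre at least 4 times the reference titre, with a reference below LLOQ set to 5 (threshold 20). State that this also covers the previous-visit comparisons from Y1, where the threshold is otherwise 20 or 40 depending on the value chosen.
3. **Protocol 8.1.2.2.** Reword the 40-or-more sentence as at least 4 times the observed baseline, which is 40 only when the baseline is exactly 10.

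The cost is a few lines of text and a small change to the derivation code. The one real downside is that GMTRs would no longer be directly comparable with any earlier study that used LLOQ in the denominator unless those are re-derived; the footnote option under item 1 avoids this.

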#### 4.2.1.2 Seroprotection

See Section 4.1 (or Section 8.1.2 of the protocol).

## 4.2.1.3 Seroconversion

See Section 4.1 (or Section 8.1.2 of the protocol).

#### 4.2.1.4 Baseline Serostatus

The baseline serostatus (eg, YF naïve participants and YF immune, Dengue naïve and Dengue immune, Zika naïve and Zika immune in EU and Asia; JE-naïve and immune in Asia) is defined as the presence of antibodies (Abs) in the baseline blood sample collected at Visit 1 (V01) in the present study from all participants.

YF naïve participants are participants with baseline YF NAb value below the threshold for protection [< 10 (1/dil)]. If the NAb value is  $\geq$  10 (1/dil) then the YF immune indicator will be "Immune". Otherwise, the baseline YF serostatus will be classified as "Undetermined".

Dengue serostatus at baseline will be determined using a Dengue Plaque Reduction Neutralization Test (PRNT) assay for dengue serotypes 1 to 4. The serostatus of dengue is computed based on values of dengue NAb titers against each of the four serotypes at V01. If the NAb value is positive ( $\geq 10 [1/dil]$ ) for any serotype, then the dengue immune indicator will be "Immune". Else if the NAb value is not positive (<10 [1/dil]) and non-missing for all four serotypes (ie, all of the titers planned to be measured at baseline must be available, and valid [not coded "NR" in the serology database] then the dengue immune indicator will be "Naive". Otherwise, the baseline serostatus will be classified as "Undetermined".

Zika serostatus will be determined using a Zika microneutralization test for serum samples obtained at baseline. Zika immune samples were defined as having a Zika antibody titer of  $\geq$  100 (1/dil) (1). If the NAb value is not positive (< 100 [1/dil]) and non-missing (ie, the titers planned to be measured at baseline must be available, and valid [not coded "NR" in the serology database]), then the Zika immune indicator will be "Naive". Otherwise, the baseline Zika serostatus will be classified as "Undetermined".

JE serostatus will be determined using a JE PRNT assay for serum samples obtained at baseline. JE immune samples are defined as having a JE antibody titer of  $\geq 10$  (1/dil). If the NAb value is not positive (< 10 [1/dil]) and non-missing (ie, the titers planned to be measured at baseline must be available, and valid [not coded "NR" in the serology database]), then the JE immune indicator will be "Naive". Otherwise the baseline JE serostatus will be classified as "Undetermined".

Flavivirus immune participants at baseline are defined as participants either immune to YF or immune to Dengue or immune to Zika at baseline (as well as JE in Asia). Flavivirus naive participants at baseline are defined as participants naïve to YF and naive to Dengue and naive to Zika at baseline (as well as JE in Asia). Otherwise the baseline Flavivirus serostatus will be classified as "Undetermined".

## 4.2.2 Safety

The following terms are generally used in safety tables:

- AE: Adverse event includes immediate, solicited, and unsolicited (including non-serious and serious adverse events)
- Adverse Event of Special Interest (AESI): Is one of scientific and medical concern specific to the Sponsor's product or program, for which ongoing monitoring and rapid communication by the investigator to the sponsor can be appropriate. The following AESIs have been defined for VYF03 based upon the prior experience with YF vaccines:
  - Serious hypersensitivity/allergic reactions
  - Organ failure/serious viscerotropic events
  - Serious neurologic events

- Adverse Reaction (AR): Corresponds to related AE to the study vaccine, unless otherwise specified.
- Immediate: Unsolicited systemic AE checked "Yes" in the field of "immediate (within 30 minutes from the vaccination)" by the investigator in the case report form (CRF).
- Medically-Attended Adverse Event (MAAE): New onset or a worsen of a condition that prompts the participant or participant's parent/guardian to seek unplanned medical advice at a physician's office or Emergency Department.
- Solicited reaction: Event pre-listed in the CRF, and which occurred during the solicited period
- Unsolicited AE: AE recorded in the CRF as Unsolicited Systemic Events or Unsolicited Injection Site Reactions.
- Unsolicited injection site reactions are to be considered as related to the vaccine injection and therefore analyzed as ARs.
- Unsolicited AEs occurring before or after the defined period will be presented in a separate listing.
- SAE: Unsolicited AE considered serious by the investigator (reconciled with Global Pharmacovigilance database).

## 4.2.2.1 Solicited Reactions

Solicited injection site reaction will be collected within 7 days after vaccination.

Solicited systemic reactions will be collected within 14 days after vaccination.

## 4.2.2.1.1 Daily Intensity

All daily records for solicited reactions will be derived into daily intensity according to the following classification: None, Grade 1, Grade 2, Grade 3, or Missing (Unknown).

For measurable injection site reactions:

- None: > 0 to < 25 mm
- Grade  $1: \ge 25$  to  $\le 50$  mm
- Grade  $2: \ge 51$  to  $\le 100$  mm
- Grade 3: > 100 mm

For Fever:

- None: < 38.0°C or <100.4°F
- Grade  $1: \ge 38.0^{\circ}$ C to  $\le 38.4^{\circ}$ C or  $\ge 100.4^{\circ}$ F to  $\le 101.1^{\circ}$ F
- Grade 2:  $\geq$  38.5°C to  $\leq$  38.9°C or  $\geq$  101.2°F to  $\leq$  102.0°F
- Grade  $3: \ge 39.0^{\circ}$ C or  $\ge 102.1^{\circ}$ F

For the derivation of daily intensities, the following sequential steps will be applied:

- 1) Solicited reactions (except Fever/Pyrexia) with CRF presence recorded as "No" and with all daily records missing (Unknown) then all daily intensities will be derived as None.
- 2) For non-measurable solicited reactions, daily intensities will correspond to daily records reported in the clinical database. For measurable solicited reactions the daily measurements reported in the clinical database will be converted based upon the intensity scales defined in the protocol; this assumes a reaction that is too large to measure (non-measurable, "NM") is Grade 3. Note the intensity could be considered "None" (not a reaction) in the analysis despite being considered a reaction by the investigator (eg, swelling measurement > 0 mm but < 25 mm in adults).

Note: The maximum intensity on the ongoing period is derived from the record of the maximum intensity/measurement after the end of the solicited period following the rule described above.

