## 4.2.2.1.2 Maximum Overall Intensity

Maximum overall intensity is derived from the daily intensities computed as described in Section 4.2.2.1.1 and is calculated as the maximum of the daily intensities over the period considered.

Note: The maximum intensity could be considered "None" (not a reaction) in the analysis despite being considered a reaction by the investigator (eg, swelling measurement > 0 mm but < 25 mm in adults).

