#### 4.2.2.1.3 **Presence**

Presence is derived from the maximum overall intensity over the time period considered:

- None: No presence
- Grade 1, Grade 2, or Grade 3: Presence
- Missing or Unknown: Missing presence

Participants with at least one non-missing presence for a specific endpoint will be included in the analysis. Conversely, those without a non-missing presence will not be included in the analysis of the endpoint.

The time period is displayed as follows:

- Injection site reactions: D1-D4, D5-D8, D9 or later
- Systemic reactions: D1-D4, D5-D8, D9-D15, D16 or later.

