#### 5.3.2.4 Intensity

For solicited reactions, missing intensities will be handled as described in Section 4.2.2.1.1. For unsolicited AEs, missing intensities will remain missing and will not be imputed.

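### The SAP has no rule for a solicited reaction recorded as present with no daily records, so known cases of pain, headache, malaise or myalgia drop out of their single-symptom rates

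*SAP*

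**What the plan says.** SAP 4.2.2.1.1 derives daily intensities in two steps.

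- Step 1 covers solicited reactions other than fever. Those "with CRF presence recorded as 'No' and with all daily records missing (Unknown) then all daily intensities will be derived as None".
- Step 2 covers the rest. "For non-measurable solicited reactions, daily intensities will correspond to daily records reported in the clinical database". Measurable reactions are graded from the daily measurements.

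Maximum overall intensity (SAP 4.2.2.1.2) "is calculated as the maximum of the daily intensities over the period considered". Presence (SAP 4.2.2.1.3) is then read from that maximum, with the entry "Missing or Unknown: Missing presence", and "those without a non-missing presence will not be included in the analysis of the endpoint".

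The missing-data section adds nothing for this case. SAP 5.3.2 states a general policy of no replacement. SAP 5.3.2.4 says: "For solicited reactions, missing intensities will be handled as described in Section 4.2.2.1.1". SAP 5.3.2.3 makes the same cross-reference for measurements. In the shells of Tables 7.8 and 7.9, M counts participants with available data for the endpoint.

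**The concern.** The CRF presence question is used in one direction only. A 'No' without daily records is believed and counted; a 'Yes' without daily records is not. Protocol 8.3.2 shows how the second case can arise: sites interview participants and may enter information that the diary card does not contain, so a reaction can be reported without daily grades.

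For pain, headache, malaise and myalgia, Grade 1 in Protocol Tables 10.1 and 10.2 already covers a reaction that does not interfere with usual activities. A true 'Yes' is therefore at least Grade 1. Only the grade is unknown, not the event.

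Elsewhere the SAP keeps events whose details are missing. An unsolicited AE needs a verbatim term and must not be Grade 0, so a missing grade does not remove it (4.2.2.2.1). Missing causality counts as related (5.3.2.2), and missing onset is included (4.2.2.2.4). The solicited 'Yes' without daily records is the exception.

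At stake is the description of reactogenicity against Stamaril, which is part of a secondary objective.

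**Working it through.** The plan states no figure on this point, so there is none to reproduce.

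**Path of a participant with all daily records missing, for a non-measurable reaction**

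| SAP section | CRF 'No' | CRF 'Yes' |
|---|---|---|
| 4.2.2.1.1, step 1 | every day None | not covered |
| 4.2.2.1.1, step 2 | not needed | every day Missing |
| 4.2.2.1.2 | maximum None | maximum Missing |
| 4.2.2.1.3 | not present, in M | presence missing, not in M |

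The exclusion of 'Yes' follows from combining these sections; no single sentence states it.

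**Single-symptom any-grade rate.** Let p be the true share with the reaction and m the share of those with no daily records. Neither is in the documents; the values below are assumptions.

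- Numerator under the SAP: p(1-m).
- Denominator under the SAP: 1-pm, because only the 'Yes' participants without records leave.
- Reported rate: p(1-m)/(1-pm).

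At p = 50% and m = 5%: 0.475/0.975 = 48.7%.

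| True rate p | m = 2% | m = 5% | m = 10% |
|---|---|---|---|
| 10% | 9.8% | 9.5% | 9.1% |
| 30% | 29.6% | 28.9% | 27.8% |
| 50% | 49.5% | 48.7% | 47.4% |
| 70% | 69.6% | 68.9% | 67.7% |

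The largest shortfall here is 2.6 points (p = 50%, m = 10%). At m = 0 it is zero.

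**In participants**, with the planned 460 and 230 (SAP 5.5), p = 50% and about 5% of reactors without records:

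- vYF: 230 reactors, 12 dropped, 218/448 = 48.7% against 230/460 = 50.0%.
- Stamaril: 115 reactors, 6 dropped, 109/224 = 48.7% against 115/230 = 50.0%.

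**Between arms.** With equal p and m the difference is zero, as above. If m were 10% for vYF and 2% for Stamaril with p = 50% in both, the rates would be 47.4% and 49.5%, a false difference of -2.1 points.

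**Composite rows.** The solicited rows of Tables 7.8 and 7.9 are composites (any, injection site, systemic, and in Table 7.9 their Grade 3 versions). A participant with 'Yes' but no daily records for one symptom may still have non-missing presence for another.

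- If another symptom is graded, the participant is correctly counted as a reactor.
- If all the others are None, the participant may stay in M as a non-reactor. Taking p as the true composite rate and m as the share of its reactors in this position, the rate is p(1-m): 0.50 × 0.95 = 47.5% at m = 5%.

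**Erythema and swelling.** A 'Yes' below 25 mm is analysed as None, so the direction is not fixed. If 30% of 'Yes' reactions reach 25 mm, 50% report 'Yes' and measurements are missing for 5% of 'Yes' regardless of size, the rate is 0.3 × 0.475/0.975 = 14.6% against a true 15.0%. If instead 30 of 460 truly reach 25 mm and 10 more have unmeasured reactions below 25 mm, the SAP gives 30/450 = 6.7% against 30/460 = 6.5%.

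**The case against.** The strongest reply is that the gap will be nearly empty. The same interviews in Protocol 8.3.2 are meant to clarify incomplete entries, and source data verification (Protocol 10.1.7) and review before database lock (SAP 5.6) follow. Even at m = 5% and p = 50%, the 1.3-point shift is well inside a 95% CI half-width of 1.96 × √(0.25/460) = 4.6 points. The safety analysis tests no hypothesis, and the shells print N and M, so exclusions from M can be seen. All of this limits the size, and it stands. It does not supply the missing rule, and M would not show that the excluded participants were reactors.

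A reader might also infer more than the documents support:

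- **That every solicited rate is affected.** Step 1 begins "Solicited reactions (except Fever/Pyrexia) with CRF presence recorded as 'No' and with all daily records missing (Unknown) then all daily intensities", so for fever 'No' and 'Yes' with no daily records are both left missing. There is no asymmetry for fever.
- **That these participants always leave both numerator and denominator in Tables 7.8 and 7.9.** Those rows are composites, and the participant may stay in M, counted rightly or wrongly.
- **That the bias is always downward.** It is for the any-grade rates of the four non-measurable reactions. For erythema and swelling it can go either way. A Grade 3 rate can rise if the dropped reactors were Grade 1 or 2, because only its denominator shrinks.
- **That 'No' with blank days means a lost diary and should be set to missing.** The CRF is not in the documents. Daily fields may simply stay blank after 'No', while temperature is recorded every day; that would also explain the fever exception. Removing such participants could take out many true non-reactors and inflate the rates.

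**Conclusion.** The rule is incomplete and, for pain, headache, malaise and myalgia, gives a wrong result: a participant known to have reacted is removed, and the single-symptom any-grade rate is biased downward whenever m is above zero and p is below 100%. This rests on the SAP's derivation sections and on taking a CRF 'Yes' as a true reaction within the solicited period.

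The size depends on m, which the documents do not give. Over the assumed range of 2% to 10%, with p from 10% to 70%, the shortfall is 0.2 to 2.6 points; in practice it is probably near the lower end. The arm difference is unchanged if p and m are equal in both arms. Only descriptive secondary safety results are touched; the primary non-inferiority test is not. The change is worth making because it is cheap and brings solicited reactions into line with how the SAP treats other incompletely described events.

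**What to change.** Add a step to SAP 4.2.2.1.1, mirrored in 4.2.2.1.3: for injection site pain, headache, malaise and myalgia, CRF presence 'Yes' with all daily records missing counts as present, in both n and M and in the any-grade composite rows, with intensity Missing. Leave these participants out only of the by-grade, onset and days-of-occurrence rows. The any-grade rate for each of the four then returns to p, for example 230/460 = 50.0% instead of 218/448 = 48.7%. Grade 3 rows are unchanged by this step.

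For erythema and swelling, keep the 'No' rule as written and report by arm how many participants have 'Yes' but no measurement. Fever needs no change on this point.

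The cost is one derivation rule and one count. The downside is slightly higher reported reaction rates and a small category with intensity missing.
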